g) **Sequencing and analytical methods.** Using resources available in the UIUC-Mayo consortium, two complementary approaches will be utilized to analyze stool specimens from each subject. First, microbial DNA will be extracted from stool and tissue samples using standardized methods [33]. Phylotype profiles of the microbiome from control and constipated populations will be generated using deep rDNA hypervariable tag sequencing of the hypervariable V3-V5 region of the SSU rRNA gene, which has been validated for use with human microbiomes and is one of the methods of choice for the HMP. With the longer reads from the MiSeq (250x250 paired end reads), our sequencing will include both the V3-V5 RGTs making for a more optimal phylogenetic analysis [34]. Phylotype profiles of the mucosa-associated microbiome will be generated using rDNA sequencing of the hypervariable V3-V5 region, which has been validated for standard use by the human microbiome project. The 300 base pair reads will ensure a better optimal phylogenetic identification. Barcoding samples prior to sequencing will yield approximately 20,000 reads/sample, ensuring detection of both dominant (core microbiome) and poorly represented taxa (variable microbiome). Identifying the existent taxa, diversity, and ecological relationships within each sample requires that we process large volumes of 16S DNA sequence data. In order to accomplish this task we will follow protocols that we have quantitatively shown to be optimal. Paired end reads will be stitched, aligned, and classified using a custom pipeline (TORNADO v2.0).[35] Briefly, low base quality reads will be either trimmed or discarded,[36] and these reads will not be classified as a bacteria kingdom[37] or matched to the bacteria 16S rRNA secondary structure.[38] To evaluate the microbial diversity and abundance, UPARSE will be used for Operational Taxonomical Units (OTU) clustering,[39] and FastTree for phylogeny.[40] The 16S data will be clustered into OTUs at 97% sequence similarity, and the taxonomy will be assigned using the Ribosomal Database Project classifier. h) Effects of alfuzosin in bowel habits (Part B). During the first 2 weeks, bowel habits will be recorded at baseline. During the next 2 weeks, patients will be treated (double-blind) with placebo or alfuzosin (10 mg) ER once daily, which is FDA-approved dose for urinary symptoms. Symptom assessments are shown in Table 1 and in Appendices 1-5. Per eligibility criteria, subjects will discontinue medications which can affect GI transit during the baseline and treatment periods. Patients who need rescue medication, after three full days without a bowel movement, can receive 1-2 bisacodyl 5 mg tabs or a bisacodyl suppository (10 mg) or up to Fleet's enemas. In addition, patients who need relief of mild pain can use analgesic drugs such as NSAIDs and COX-2 inhibitors for up to two doses per week. During the procedure, intake of acetaminophen up to 1.5g per day in divided doses will be permissible.

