
#### 4. Data and statistical analysis

a) Part A. Anal manometry will be analyzed by established techniques and summarized as anal resting and squeeze pressures, rectal and anal pressure and rectoanal gradient during evacuation. Rectal pressure-volume relationships will be summarized by the  $P_{r_{half}}$  during rectal compliance, rectal capacity, pressure and volume sensory thresholds for first sensation, desire to defecate, and urgency. During

sinusoidal oscillation, average rectal pressures and the variability in pressures over 20 min will be summarized.

The analysis will be based on analysis of covariance (ANCOVA) models to assess the pre-dug period for intervention effects with subject status and intervention type as the primary factors (a check for order effects of the intervention sequences will also be made, and the corresponding pre-stress response will be included as a covariate). Models with a subject status by intervention type interaction will also be examined. During period 2, subjects will have been randomized to drug or placebo (balanced on subject status) and use the same intervention sequence as the pre-drug period). The analysis of the post drug period will also be based on ANCOVA models incorporating subject status, intervention type, treatment group, and corresponding interactions (a check for order effects will again be made). The corresponding responses from the pre-stress interval from period 1 and VAS scores for stress and arousal will be used as covariates,

b) Part B.

- i. Endpoints. Symptoms and Signs of Chronic Constipation. The effects of alfuzosin compared to placebo will be assessed by evaluating
  - Bowel habits using a daily diary (Appendix 1) to record stool consistency (Bristol Stool Form scale), frequency, ease-of-passage and sensation of complete bowel emptying (yes/no)
  - Daily Abdominal Pain Scores (Appendix 2) collected as (a) most severe daily score and (b) overall average daily score).
  - Global Patient Treatment Assessments reporting outcomes on a weekly basis (Appendix 3) including overall relief and severity of constipation
  - Global Patient reported outcomes on a 2-week basis (Appendix 5)
  - Patient reported outcomes of other abdominal symptoms (Appendix 6)

Two outcomes will be derived from primary data.

  - Weekly rate of SBMs: a bowel movement (BM) is considered an SBM if no laxative, enema or suppository was taken in the preceding 24 hours.

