  - Weekly rate of CSBMs: if the patient indicated that the SBM was associated with a sensation of complete bowel emptying, the SBM will be counted as a CSBM.
- ii. Analysis. Daily bowel diary responses will first be averaged over study periods (baseline and treatment) and in the case of stool frequency, per week. These responses will also be assessed using ANCOVA models, with the corresponding baseline value as the primary covariate. For stool frequency, the two weekly values will be assessed using a repeated measures ANCOVA model with the overall average baseline stool frequency value as a covariate. The global assessment scores (adequate relief and severity) will first be summed over the two treatment weeks, and then assessed using the Wilcoxon rank sum test. Individual adverse events (AEs) will be summarized by treatment group and the overall total frequency (per subject) of AEs assessed using the Wilcoxon rank sum test. The analyses will follow the intent to treat (ITT) paradigm with all

- patients randomized included in the analyses. Patients with missing values for a particular endpoint will have their missing values imputed using the corresponding overall mean value from all patients with non-missing data for that endpoint. An adjustment in the ANCOVA error degrees of freedom (subtracting one for each imputed value) will be made to account for the imputation. A similar adjustment for the Wilcoxon rank sum test (adjusting the degrees of freedom for the t-approximation) will also be examined.

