5. Sample size assessment. The sample size assessment is based on the variation in anal resting pressures in healthy subjects and patients with defecatory disorders and the effect of the  $\alpha_1$  receptor antagonist (indoramin) on anal resting pressure in a previous study. The CV (%) in anal resting pressure evaluated by the same technique in healthy women (<50 years old) and patients with defecatory disorders (<50 years old and resting pressures >90) was 20% (mean=93.7{SD=18.5}) and 11% (mean=102.9{SD=11.7}), respectively. In period 2 the sample size of 36 controls and 36 patients will yield 18 subjects per treatment arm (drug vs. placebo) in each subject group (control vs. patients). This should provide 80% power to detect a treatment effect size of roughly 15-20%, based on a two sample t-test with a two-sided alpha level of 0.05 separately in each subject group. The effect size is defined as the difference in group means as a percentage of the overall (both groups) mean value. The previous study suggested an effect size of 47% for drug effects. For part B, data pooled from constipation subjects imply differences between treatment groups of ~4 stools per week, differences in stool consistency scores of ~1.1 and differences in ease of passage scores of 0.8 could be detected with 80% power (2-sided alpha level of 0.05). It is anticipated that the ANCOVA models will provide similar power for somewhat smaller differences by incorporating the baseline values as covariates.
  6. Anticipated results and interpretation. We anticipate that: (i) alfuzosin will reduce anal resting pressure and increase the rectoanal gradient during simulated evacuation but not affect the squeeze increment; (ii) alfuzosin will attenuate the augmentation of anal pressure by mental stress; (iii) mental relaxation will reduce anal resting pressure to a greater extent after placebo than alfuzosin; and (iv) rectal compliance and the contractile response to sinusoidal oscillation will be lower in chronic constipation than in healthy subjects.

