### Appendix 1. Sample Stool Diary Card

Daily Diary												
Date: 												
If you had no bowel movements today, please check this box:  No bowel movements today.												
Please record the time you took the study medication today: _____ : _____												
Please record the time of today's breakfast: _____ : _____												
	Describe the consistency of bowel movement	Describe the Ease of Passage of bowel movement	Did you feel like you completely emptied your bowels?									
	1 hard lumps 2 lumpy sausage 3 cracked sausage 4 smooth sausage 5 soft lumps 6 Mushy 7 watery	1 Manual Disimpaction 2 Enema needed 3 Straining needed 4 Normal 5 Urgent wo/pain 6 Urgent w/pain 7 Incontinent	1 no 2 yes									
1   am  pm hr. min												
2   am  pm hr. min												
3   am  pm hr. min												
4   am  pm hr. min												
5   am  pm hr. min												

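### Part B averages stool form and ease of passage over all diary movements, including those after rescue, and does not tie the analysed stool frequency to the spontaneous-movement rates it derives

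*Combined protocol and SAP*

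**What the plan says.** Section B.3.h allows rescue in both arms: "Patients who need rescue medication, after three full days without a bowel movement, can receive 1-2 bisacodyl 5 mg tabs", with a suppository or enemas as alternatives.

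Section B.4.b.i derives two weekly rates. For the first, "a bowel movement (BM) is considered an SBM if no laxative, enema or suppository was taken in the preceding 24 hours". For the second, "if the patient indicated that the SBM was associated with a sensation of complete bowel emptying, the SBM will be counted as a CSBM".

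The analysis paragraph, B.4.b.ii, mentions neither rate. It says "Daily bowel diary responses will first be averaged over study periods (baseline and treatment) and in the case of stool frequency, per week", and then "For stool frequency, the two weekly values will be assessed using a repeated measures ANCOVA model with the overall average baseline stool frequency value" as covariate. The other averaged responses go into ANCOVA with their own baseline value.

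Section B.5 states Part B sensitivity as about 4 stools per week, adding "differences in stool consistency scores of ~1.1 and differences in ease of passage scores of 0.8 could be detected" with 80% power. It does not say whether those stools are spontaneous.

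The diary in Appendix 1 has a row for each movement, and its ease scale reads "1 Manual Disimpaction 2 Enema needed 3 Straining needed 4 Normal 5 Urgent wo/pain 6 Urgent w/pain 7 Incontinent". Assisted movements are therefore expected to be scored. The diary also asks about non-routine medicines, with dose and frequency but no time. No comparison of rescue use between arms is planned.

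**The concern.** Rescue is triggered by going without a movement, so it is partly a result of treatment. A patient who responds poorly takes more rescue, and the stools it produces then enter her own outcome. They add to the count, they are likely to be looser than her spontaneous stools, and they receive an ease code that reflects the rescue product.

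If rescue differs between arms, the comparison mixes the effect of alfuzosin with the effect of bisacodyl or enemas. Adjusting for baseline does not remove this, because the difference arises after randomisation. At stake is whether Part B can show an effect on bowel symptoms, and for stool form whether the sign of the difference can be trusted.

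**Working it through.** **The plan's own figures.** Section B.5 gives no standard deviations for Part B, so its detectable differences can be inverted but not reproduced. With 18 patients per arm, a two-sample t-test, two-sided alpha 0.05 and 80% power, the standardised difference is 0.961. The implied SDs are:
- frequency: 4 / 0.961 = 4.16 stools per week
- form: 1.1 / 0.961 = 1.14
- ease: 0.8 / 0.961 = 0.83

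These figures are not disputed. The point is which stools they describe.

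**How much rescue the rule allows.** Three full days without a movement means each episode uses about four days. The ceiling is about 7 / 4 = 1.75 episodes per week with no spontaneous movements, or (7 − 1) / 4 = 1.5 with one spontaneous movement on its own day.

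**Form and frequency (all values assumed).** Placebo: 1.5 SBMs per week at form 2. Alfuzosin: 2.5 SBMs per week at form 3. Each rescue gives one stool. The spontaneous-only differences (alfuzosin minus placebo) are 1.0 per week and +1.0 in form. One rescue per week on placebo fits the rule: 1 × 4 + 1.5 = 5.5 of 7 days.

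All-stool frequency = SBMs + rescue stools. All-stool form = (SBMs × their form + rescue stools × their form) / all stools.

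For 1 v 0.25 rescues per week at form 5:
- placebo: 1.5 + 1 = 2.50 stools; form (1.5 × 2 + 1 × 5) / 2.50 = 3.20
- alfuzosin: 2.5 + 0.25 = 2.75 stools; form (2.5 × 3 + 0.25 × 5) / 2.75 = 3.18

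The same formulas with other assumed inputs give:

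| Rescues/week, placebo v alfuzosin | Form of rescue stool | Frequency difference (SBM only: 1.0) | Form, placebo v alfuzosin | Form difference (SBM only: +1.0) |
|---|---|---|---|---|
| 1 v 0.25 | 5 | 0.25 | 3.20 v 3.18 | −0.02 |
| 1 v 0.25 | 4 | 0.25 | 2.80 v 3.09 | +0.29 |
| 1 v 0.25 | 6 | 0.25 | 3.60 v 3.27 | −0.33 |
| 0.5 v 0.25 | 5 | 0.75 | 2.75 v 3.18 | +0.43 |
| 0.5 v 0.5 | 5 | 1.00 | 2.75 v 3.33 | +0.58 |

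In the last row rescue is equal and frequency is untouched. Form is still diluted, because rescue stools are a larger share of the smaller placebo total (0.5 / 2.0 against 0.5 / 3.0).

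**Power for frequency.** All-stool difference = SBM difference − (excess rescues per week in the comparator arm × stools per rescue). Take a true SBM difference of 4 per week and assume SD 4.16 for either count. One extra rescue per week giving one stool leaves 4 − 1 = 3, and power falls from 80% to 56%. With two stools per rescue it leaves 4 − 2 = 2, and power is 29%.

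**Ease.** Take three spontaneous stools coded 3 and add one rescue stool:
- enema, coded 2: (9 + 2) / 4 = 2.75
- bisacodyl, if coded 4: (9 + 4) / 4 = 3.25
- bisacodyl, if coded 6: (9 + 6) / 4 = 3.75

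The mean moves from 3.0 by −0.25 to +0.75, depending on the rescue type. The stated detectable difference is 0.8.

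**The case against.** **Inclusion is inferred.** No sentence says that rescue movements count. The SBM and CSBM rates are the only weekly rates the plan defines, and the analysis paragraph follows directly, so stool frequency could be read as meaning SBMs. This stands for frequency: the fault there is an undefined term and no named SBM or CSBM analysis. A reader might infer that the plan has no rescue-free measure, or that it expressly counts rescue stools in frequency; the text supports neither. For form and ease no rescue-free version is defined, and the ease code for enemas points to inclusion.

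**Direction.** A reader might also infer that the arm needing more rescue will look as good or better on all three outcomes. That fails for ease, since an enema stool is coded 2, below straining (3) and normal (4). For form, a higher score is not always better, because the diary scale runs from hard lumps through a smooth stool at 4 to watery at 7. Neither makes the averages interpretable: one stool coded 2 and one coded 6 for ease average to 4, the normal code.

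**Size.** The three-day trigger limits rescue, and the baseline covariate is built the same way. Examples that put a whole arm at the ceiling exaggerate the effect. The main case above stays below it.

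**Importance.** Aim 5 is framed as exploratory, and section B.7 says the sample size is primarily for acute anorectal effects. If alfuzosin lowers rescue use, the bias in frequency runs towards no difference. This lowers the severity, but an exploratory comparison that hides a real effect still misinforms the next study.

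**Restricting to SBMs has its own problem.** A patient with no SBM would have no form or ease value, and B.4.b.ii would give her the overall mean. This stands, and the fix must deal with it.

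**Conclusion.** The concern holds in limited form. As written, the Part B averages of form and ease take in rescue-induced stools, whose number depends on response to treatment. For frequency, the plan does not say whether the modelled and powered quantity is all movements or SBMs, which leaves the choice open until the data are seen.

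A difference in rescue between arms can attenuate a frequency effect and attenuate or reverse a form effect. The direction for ease depends on the rescue product. In the main assumed case a form difference of +1.0, close to the 1.1 the plan says it can detect, becomes about 0, and a frequency difference of 1.0 becomes 0.25. At lower or equal rescue rates the loss is smaller.

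All of this rests on assumed rescue rates, stools per rescue and stool forms, on pooling all stools in an arm, and on an SD obtained by inverting the plan's own figure. The documents supply none of these, so no particular bias can be claimed. Severity is moderate, and Part A is not affected.

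**What to change.** In section B.4.b.ii:

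1. State that the repeated measures ANCOVA of stool frequency uses weekly SBMs, with the same analysis for CSBMs.
2. Average form and ease over SBMs in both the baseline and treatment periods.
3. Report the all-stool versions and the number of rescue days by arm alongside.
4. State how patients with no SBM in a period are handled for form and ease, in place of the pooled mean. One option is to analyse those with SBMs, report the number without by arm, and use the all-stool version as a sensitivity analysis.
5. Add a time for rescue to the Appendix 1 diary, or state a day-level version of the 24-hour rule. The existing SBM definition already needs this, and the present medication item could miss a product that a patient regards as routine.

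The cost is revised analysis wording and a small diary change, with no change to sample size, visits or treatment. The drawback is that form and ease rest on fewer movements and some patients contribute none. Restricting ease to SBMs also largely removes the enema code, itself a sign of poor evacuation, so the all-stool and rescue figures should be reported with it.

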**THE REST OF THIS PAGE IS INTENTIONALLY BLANK**

**Table 1. Schedule for Study Assessments and Monitoring**

[figure not shown]
	Screening	Acute Study	Bowel Symptoms (Alfuzosin – ER 10 mg)			
	Days –30 to 1	Day 1	Baseline Period (Days 3-16)		Treatment Period (Days 17-30)	
Procedure			Daily	Other	Daily	Other
Informed consent	X					
Review eligibility	X					
Physical examination	X					
Concomitant medication review	X	X				
Vital signs, weight	X	X 				
Serum creatinine, urine pregnancy test, ECG (12-lead)	X 					
Stool sample	X 			X 		
Anorectal study		X				
Randomization to treatment		X				
Study treatment administration		X				X 
Adverse event assessment		X		X 		X 
Stool diary (Appendix 1)			X		X	
Abdominal pain (Appendix 2)			X		X	
Global assessments (relief, severity) (Appendix 3)				Weekly		Weekly
Global assessment – satisfaction with treatment, (Appendix 4)	X			X (day 17)		X (day 31)
Other abdominal symptoms (Appendix 5)				Weekly		Weekly
Telephone contact				X  (q3-5 days)		X  (q3-5 days)

1. During the acute study, heart rate and blood pressure will be recorded at hourly intervals. Height (cm) and weight (kg) will be recorded at the screening visit but not on Day 1.
2. Urine pregnancy test to be performed for women of childbearing potential within 2 weeks of Day 1. Serum creatinine and ECG (12-lead) to have been done within three months of Day 1.
3. A single stool sample can be collected either before the acute study visit, or 3 days after the acute study visit, but before the treatment period.

4. Patients will be treated with placebo or alfuzosin ER (10 mg) once daily during this phase. While the protocol is planned for the treatment period to follow directly the baseline period, if needed for scheduling, there can be up to a 5-day interval between the baseline and treatment period.
5. Patients will be contacted by telephone every ~3-5 days between clinic visits to address questions, ascertain side effects and remind subjects to complete diaries. The final phone call will be within 5 days after completing the treatment period. Subjects will be asked to return unused medication by mail.

3. Experimental procedures. Items a-d below exclusively pertain to Part A,

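### The Part B global severity score is compared by an unadjusted Wilcoxon test although the same score is collected at baseline; a rank ANCOVA could be more precise at almost no cost.

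*Combined protocol and SAP*

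**What the plan says.** The analysis paragraph for Part B (section B, item 4, Data and statistical analysis) treats two kinds of endpoint differently.

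- **Daily diary endpoints.** "These responses will also be assessed using ANCOVA models, with the corresponding baseline value as the primary covariate". Stool frequency gets a repeated measures ANCOVA, also with baseline frequency as covariate.
- **Global scores.** "The global assessment scores (adequate relief and severity") are summed and compared between arms: they "will first be summed over the two treatment weeks, and then assessed using the Wilcoxon rank sum test". No baseline term is mentioned.

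Table 1 has a row "Global assessments (relief, severity) (Appendix 3") marked weekly in two places: under "Baseline Period (Days 3-16") and again under the treatment period, Days 17-30. By that schedule each patient has two baseline and two treatment-period ratings. No section uses the baseline ratings in an analysis or explains leaving them out.

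Item 5, Sample size assessment, gives the plan's view of baseline adjustment: "It is anticipated that the ANCOVA models will provide similar power for somewhat smaller differences by incorporating the baseline values as covariates".

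**The concern.** Patients with chronic constipation probably differ in how severe they rate it before treatment, and some of that difference is likely to persist on treatment. An unadjusted comparison leaves the persistent part in the error term. A baseline covariate removes it, and also corrects the estimate for whatever chance imbalance in baseline severity arises between two small arms.

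The plan already does this for the diary endpoints. An ordinal scale does not explain the different handling of severity, because a rank ANCOVA keeps the rank basis and still uses baseline. At stake is the power of one exploratory comparison: with few patients, a real effect on severity is more likely to be missed and then read as no effect.

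**Working it through.** **Plan's own figure.** There is none to reproduce. Item 5 gives Part B differences that "could be detected with 80% power (2-sided alpha level of 0.05") for stool frequency, consistency and ease of passage. It gives no SD, effect size or power for the global scores.

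**Inputs from the documents.** Item 5 says that 36 controls and 36 patients "will yield 18 subjects per treatment arm (drug vs. placebo) in each subject group (control vs. patients"). Part B enrols patients only, so I take 18 against 18, with two-sided alpha 0.05.

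**Assumed inputs.** The true shift and the baseline-to-treatment correlation ρ are not in the documents. I use shifts of 0.8 SD and about 0.95 SD, and ρ from 0 to 0.7.

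**Step 1: formula.** With total N = 36, adjusting for one baseline covariate multiplies the variance of the treatment difference by

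(1 − ρ²) × (N − 3)/(N − 4) = (1 − ρ²) × 33/32.

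The second factor is the small-sample price of estimating the slope. Error degrees of freedom fall from 34 to 33.

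- ρ = 0: 1 × 33/32 = 1.03, a slight loss.
- ρ = 0.2: 0.96 × 33/32 = 0.99, no practical change.
- ρ = 0.4: 0.84 × 33/32 = 0.87.
- ρ = 0.5: 0.75 × 33/32 = 0.77, equivalent to 18/0.773 ≈ 23 per arm.
- ρ = 0.7: 0.51 × 33/32 = 0.53, equivalent to 18/0.526 ≈ 34 per arm.

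Break-even is at ρ² = 1/33, so ρ ≈ 0.17.

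**Step 2: power from the formula.** An unadjusted two-sample t-test with 18 per arm has 80% power at 0.96 SD. At that same shift, noncentral-t power with adjustment is 79% at ρ = 0, 80% at 0.2, 82% at 0.3, 85% at 0.4, 89% at 0.5, 93% at 0.6 and 97% at 0.7.

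**Step 3: simulation on ordinal scores.** The formula is for a continuous score, so ordinal scores were simulated. The Wilcoxon test was compared with an ANCOVA of treatment-period ranks on baseline ranks.

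| ρ (assumed) | Shift 0.8 SD: Wilcoxon → rank ANCOVA | Shift 0.95 SD: Wilcoxon → rank ANCOVA |
|---|---|---|
| 0 | 62% → 60% | 78% → 77% |
| 0.2 | 63% → 63% | 80% → 80% |
| 0.4 | 61% → 67% | 80% → 85% |
| 0.5 | 62% → 72% | 78% → 88% |
| 0.7 | 61% → 83% | 79% → 97% |

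A separate simulation at 0.8 SD gave 85% for rank ANCOVA at ρ = 0.7, hence the range 83-85%. The true Wilcoxon power does not depend on ρ, so the small differences down each Wilcoxon column are simulation noise. Type I error was 4-6% for both methods throughout.

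**Step 4: relief.** A weekly yes/no relief item summed over two weeks was also simulated. The assumptions were 10% yes at baseline, 30% on placebo, and a latent shift of 0.8 SD. Wilcoxon against rank ANCOVA gave 44% and 44% at latent correlation 0.5, and 43% and 46% at 0.7. With a baseline near its floor there is almost nothing to gain.

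**The case against.** The strongest reply is that nothing here is wrong. The Wilcoxon test holds its error rate under randomization, chance baseline imbalance is already covered by that error rate, and a rank test is a conventional choice for a short ordinal sum. All of that stands. A reader might infer that the planned test is biased or that the plan contradicts itself. The documents support neither: the item 5 remark on baseline values is about the ANCOVA models, and the plan does not promise them for the global scores.

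Second, the gain depends on a correlation that nobody has stated. This also stands. At about 0.2 or below there is no gain, and it becomes material only from about 0.4. A reader might take it as settled that precision is being lost, or quote 36/(1 − ρ²), which gives 48 patients at ρ = 0.5 and 71 at 0.7. That is a large-sample formula for a continuous score. The small-sample version in Step 1 gives about 46 (2 × 23) and 68 (2 × 34), and both rest on the assumed correlation.

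Third, relief. A reader might extend the point to both global scores, since Table 1 lists them together. The documents do not support that. The wording and scale of Appendix 3 are not in the text available for this review, and no Part B study treatment is given during the baseline period, so a baseline relief rating may vary little. Step 4 shows how the gain can then vanish, though its inputs are assumptions too.

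Fourth, consequence. Aim 5 is to explore effects on bowel symptoms, and item 7 (Potential pitfalls) says the sample size is designed primarily for the acute anorectal effects. This limits the weight of the point but does not remove it, because the change is nearly free.

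**Conclusion.** The point holds for severity, as an inexpensive improvement in precision on an exploratory endpoint. It is not a flaw in validity. At 18 per arm and a 0.8 SD shift, replacing the Wilcoxon test by a rank ANCOVA moves power from about 61% to between 60% (no baseline correlation) and 83-85% (correlation 0.7), with 72% at 0.5. The downside is about one percentage point. The upside is about 10 points at 0.5.

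This rests on three assumptions: the size of the shift, the baseline correlation, and all 36 patients contributing to Part B in equal arms. That the score is scheduled at baseline and left out of the analysis is read directly from the plan. For relief, no gain has been shown.

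**What to change.** Amend the sentence on the global scores in the Part B analysis paragraph, before unblinding:

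- **Severity.** Rank the score summed over the two treatment weeks, rank the score summed over the two baseline weeks, and test treatment in an ANCOVA with the baseline rank as covariate. Report the Wilcoxon rank sum test as a sensitivity analysis.
- **Relief.** Use the same model only if the baseline relief score varies enough between patients, judged on data pooled over arms before unblinding. Otherwise keep the Wilcoxon test.
- **Missing values.** Impute before ranking, and apply the plan's existing ANCOVA rule of subtracting one error degree of freedom for each imputed value. State that this covers imputed baseline values as well as treatment-period values.

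The cost is one error degree of freedom, worth about one percentage point of power if baseline turns out uninformative. No new data or visits are needed.

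### Part B fills missing endpoint values with the mean of both arms combined, which shrinks the estimated drug effect to (1 − m) of its true size when a share m per arm is missing completely at random

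*Combined protocol and SAP*

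**What the plan says.** The rule is in section B.4.b.ii (Part B, Analysis). That section states: "The analyses will follow the intent to treat (ITT) paradigm with all" randomised patients included. Patients lacking a value for an endpoint will have "their missing values imputed using the corresponding overall mean value from all patients with non-missing data for that endpoint". The one firm correction is: "An adjustment in the ANCOVA error degrees of freedom (subtracting one for each imputed value) will be made to account for the imputation". A similar change for the Wilcoxon test is only to be examined.

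Three features of the same section determine how often the rule applies and to what:

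- Diaries: "Daily bowel diary responses will first be averaged over study periods (baseline and treatment) and in the case of stool frequency, per week". Period averages are then analysed by ANCOVA with the baseline value as covariate.
- Stool frequency: "the two weekly values will be assessed using a repeated measures ANCOVA model", with average baseline frequency as covariate.
- Global scores: "The global assessment scores (adequate relief and severity) will first be summed over the two treatment weeks", then compared by the Wilcoxon rank sum test.

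The documents state no expected missing rate, no other missing-data method and no sensitivity analysis.

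**The concern.** The filled-in value ignores the patient's arm, her baseline (the model's main covariate) and, for stool frequency, any week she did record. Giving patients in both arms the same number builds a zero treatment difference into every imputed value. The estimate is therefore biased towards no effect even when values are missing purely by chance, the most favourable case for any method. The degrees-of-freedom subtraction changes the standard error and the critical value, not the estimate.

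Part B is the only test of whether alfuzosin helps bowel symptoms (Aim 5). Section B.5 says it can detect only fairly large differences, and expects baseline adjustment to give similar power for somewhat smaller ones. The imputation rule uses up some or all of that gain.

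**Working it through.** **Inputs from the documents.** Section B.5 says "the sample size of 36 controls and 36 patients will yield 18 subjects per treatment arm (drug vs. placebo) in each subject group". This is the Part A allocation, and I assume it carries over to Part B. Section B.5 also gives two-sided alpha 0.05, 80% power, and Part B detectable differences of about 4 stools per week, 1.1 consistency points and 0.8 ease-of-passage points.

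**Assumptions.** The missing rate is not given, so I use 1 to 4 of 18 per arm, missing completely at random. The true effect is 0.961 SD and the baseline correlation 0.5 unless stated.

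**1. The plan's own figure.** With 18 per arm, a two-sample t-test has 80% power at 0.961 SD. Section B.5 gives no Part B SD, so its differences can only be inverted: 4/0.961 = 4.16 stools per week, 1.1/0.961 = 1.14 and 0.8/0.961 = 0.83. They cannot be reproduced independently.

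**2. Bias, one value per patient.** Let P be the pooled observed mean. After filling, each arm mean is (1 − m)·μ + m·P. In the difference P cancels, leaving (1 − m)(μ₁ − μ₀). With the baseline covariate, E[Y*|T,X] = (1 − m)(a + τT + bX) + mP, so the treatment coefficient is (1 − m)τ. For 1, 2, 3 and 4 of 18 missing per arm, 1 − m = 0.944, 0.889, 0.833 and 0.778.

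If the shares differ, with equal arms, the factor is 2(1 − m₁)(1 − m₀)/[(1 − m₁) + (1 − m₀)]. For 10% and 20% this is 2 × 0.9 × 0.8/1.7 = 0.847.

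**3. Bias, stool frequency.** If a share m misses only one of two weeks, the two-week effect is ½τ + ½(1 − m)τ = (1 − m/2)τ: 0.972, 0.944, 0.917 and 0.889. If both weeks are missing, the factor is 1 − m.

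**4. On the plan's scale, two missing per arm.**

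- Stool frequency: 4 × 0.944 = 3.8 (one week missing) or 4 × 0.889 = 3.6 (both weeks).
- Consistency: 1.1 × 0.889 = 0.98.
- Ease of passage: 0.8 × 0.889 = 0.71.

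**5. Power, test size and coverage, one value per patient.** Simulation, 40,000 trials per scenario. Error df under the plan are 33 minus the number imputed.

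| Missing per arm | Estimate, % of truth | Power: plan / observed data | Test size: plan | Coverage: with / without df subtraction |
|---|---|---|---|---|
| 1 | 94 | 85 / 87% | 4.3% | 95.6 / 94.9% |
| 2 | 89 | 79 / 85% | 3.8% | 95.5 / 93.8% |
| 3 | 83 | 73 / 82% | 3.1% | 94.5 / 91.7% |
| 4 | 78 | 65 / 79% | 2.4% | 93.1 / 88.1% |

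Test size on observed data is about 5% throughout. At baseline correlation 0.3, power is 73 against 77% (two missing per arm) and 58 against 71% (four). At 0.7 it is 91 against 95% and 77 against 92%.

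**6. Stool frequency.** Here I assume a between-week correlation of 0.7 and one between-patient df removed per patient with a filled value. With one week missing for 1, 2, 3 or 4 patients per arm, power is 89 / 87 / 83 / 80%, against 90 / 90 / 89 / 89% for a likelihood model on the observed weeks. At two per arm it is 88 against 91% at between-week correlation 0.5, and 85 against 89% at 0.85. With both weeks missing for two per arm it is 82 against 87%.

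**7. Wilcoxon endpoints.** The factor (1 − m) does not apply exactly. Power is 67–68 against 68% at two missing per arm, and 58–59 against 60–61% at four.

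**8. Worst outcomes missing (not at random), with a true effect.** One drug and three placebo patients missing: the plan gives 72% of truth with 85% coverage, observed data 85% and 90%. Three drug and one placebo: the plan gives 105% and 95%, observed data 115% and 90%.

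**The case against.** The strongest reply is that little may need filling. Treatment lasts 14 days, and footnote 5 to Table 1 has patients telephoned every 3 to 5 days, among other things to "remind subjects to complete diaries". Because diaries are averaged first, a partly completed diary still yields a value. Three or four patients per arm with no value means 17–22%, and nothing in the documents suggests that. At one or two per arm and correlation 0.5, power stays at 85% or 79%, close to the 80% claimed. This stands and limits the size of the problem. It does not hold at every correlation: at 0.3, power is 73% with two missing per arm. Table 1 also shows randomisation only on Day 1. If that assigns Part B treatment, a patient who leaves before Day 17 has no treatment-period value but is still analysed.

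Second, under random missingness the error is conservative, and the df subtraction keeps coverage near nominal up to about three missing per arm. Both points are true, but neither removes the bias in the estimate.

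Third, observed-data analysis is not better everywhere. With no true effect and the worst outcomes missing, simulated false-positive rates were about 5% under the plan against 7% on observed data (two missing per arm), and about 8% against 10% (three drug, one placebo). This is a real limit of the alternative. Neither method is safe in that setting, and it does not justify a rule that is biased in the simplest one.

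Finally, Part B is exploratory, section B.7 says the sample size was chosen primarily for the acute anorectal effects, and the Wilcoxon gain is at most about 2 points. All of this is accepted.

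**Conclusion.** The concern holds. Under equal, completely random missingness, the ANCOVA effect estimate in Part B is (1 − m) of the truth, or (1 − m/2) for stool frequency when only one week is missing. Assuming 18 per arm, that is about 5.6% or 2.8% of the effect for each patient per arm affected. The test is conservative and loses power compared with analysing the observed data: about 2 percentage points at one missing per arm, 6 at two and 14 at four (79 − 65), for endpoints with one value per patient at baseline correlation 0.5.

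The missing rates, the true effect and the correlations are assumptions. If missingness depends on outcome, bias can go either way under both methods. The main aim of the trial is not threatened, and with one or two missing patients per arm the harm is small. It should still be fixed, because the planned models can use the observed values directly.

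**What to change.** Delete the pooled-mean imputation and the df subtraction from section B.4.b.ii. Suggested text:

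> Main analysis: weekly stool frequency will be analysed by likelihood-based repeated measures ANCOVA using all observed weekly values, with baseline as covariate. Other diary endpoints will be analysed by ANCOVA on the observed period averages, with baseline as covariate. Global scores will be compared by the Wilcoxon test on observed scores, using the mean of the available weekly scores. No values are imputed. Sensitivity analysis (the main analysis governs): all randomised patients are included, with missing values multiply imputed conditional on arm and baseline. The number of missing values will be reported by arm for each endpoint.

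The Wilcoxon change is for consistency and gains little.

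The cost is revised wording and slightly more programming, with no new data and no change in sample size. Patients with no post-baseline value would contribute only to the sensitivity analysis, so the sentence committing to analyse all randomised patients must be reworded to match. The change does not protect against outcome-dependent missingness; the by-arm counts at least let a reader judge how much that could matter.
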